5. STUDY TREATMENT

5.1. Formulation, Packaging, and Handling

5.1.1. BGB-DXP604

BGB-DXP604 is a neutralizing mAb formulated for intravenous injection in a single-use vial (United States Pharmacopeia [USP] type I) containing 300 mg of antibody in 10 mL of buffered isotonic solution. BGB-DXP604 has been aseptically filled in single-use vials with a rubber stopper capped with an aluminum flip-off seal. Five single-use vials are packaged into each carton. The contents of the label on vials and cartons will be in accordance with all applicable local regulatory requirements, including Annex 13 of Pharmaceutical Inspection Co-operation Scheme Good Manufacturing Practice Guide ([PIC/S GMP Guide 2018](#)).

The study drug will be dispatched to the study center only after receipt of the required documents in accordance with applicable regulatory requirements and the sponsor's procedures. The unblinded pharmacist(s) or designated personnel are responsible for maintaining the drug supply inventory and acknowledging receipt of all study drug shipments. The study drug must be stored in a secure area, with access limited to the authorized study center personnel and kept under physical conditions that are consistent with study drug-specific requirements. BGB-DXP604 must be stored at temperatures from 2°C to 8°C and protected from light.

Refer to the Pharmacy Manual for details regarding intravenous administration, accountability, and disposal. Please also refer to the [BGB-DXP604 Investigator's Brochure](#) for other details regarding BGB-DXP604.

5.1.2. BGB-DXP593

BGB-DXP593 is a neutralizing mAb formulated for intravenous injection in a single-use vial (USP type I) containing 300 mg of antibody in 10 mL of buffered isotonic solution. BGB-DXP593 has been aseptically filled in single-use vials with a rubber stopper capped with an aluminum flip-off seal. Five single-use vials are packaged into each carton. The contents of the label on vials and cartons will be in accordance with all applicable local regulatory requirements, including Annex 13 of Pharmaceutical Inspection Co-operation Scheme Good Manufacturing Practice Guide ([PIC/S GMP Guide 2018](#)).

The study drug will be dispatched to the study center only after receipt of the required documents in accordance with applicable regulatory requirements and the sponsor's procedures. The unblinded pharmacist(s) or designated personnel are responsible for maintaining the drug supply inventory and acknowledging receipt of all study drug shipments. The study drug must be stored in a secure area, with access limited to the authorized study center personnel and kept under physical conditions that are consistent with study drug-specific requirements. BGB-DXP593 must be stored at temperatures from 2°C to 8°C and protected from light.

Refer to the Pharmacy Manual for details regarding intravenous administration, accountability, and disposal. Please also refer to the [BGB-DXP593 Investigator's Brochure](#) for other details regarding BGB-DXP593.

5.1.3. Placebo

The placebo for this study is normal saline (ie, solution of 0.9% sodium chloride) at the same volume as BGB-DXP604 or BGB-DXP593. The normal saline will be sourced and provided by the site. For further details, refer to the Pharmacy Manual for the matching placebo.

5.2. Dosage, Administration, and Compliance

Planned dose level(s) for study drug(s) in each cohort are presented in [Table 4](#).

Table 4: Planned Dose Level(s) for Study Drug(s) in Each Cohort

Part 1: BGB-DXP604 Alone	Part 2: BGB-DXP604 + BGB-DXP593
Cohort 1A: 10 mg/kg BGB-DXP604 or placebo	Not applicable
Cohort 1B: 30 mg/kg ^a BGB-DXP604 or placebo	Cohort 2A: 30 mg/kg ^b BGB-DXP604 + 30 mg/kg ^b BGB-DXP593 or placebo

Abbreviation: SMC, Safety Monitoring Committee.

^a The dose level of BGB-DXP604 in Cohort 1B may be adjusted based on SMC recommendation.

^b The doses of BGB-DXP604 and BGB-DXP593 in Cohort 2A will be recommended by SMC and not exceed 30 mg/kg for each study drug.

Eligible subjects will receive the administration of study drug(s) at dose level(s) as above or matching placebo for 30 to 60 minutes.

For Cohort 2A, BGB-DXP593 infusion should be administered intravenously first, followed by the intravenous infusion of BGB-DXP604. BGB-DXP604 infusion should be given ≥ 30 minutes after the completion of the BGB-DXP593 infusion. The matching placebo for Cohort 1A and Cohort 1B is normal saline at a volume equal to BGB-DXP604 only; for Cohort 2A, normal saline solutions at a volume equal to BGB-DXP604 or BGB-DXP593 are needed and will be administered at the same sequence as BGB-DXP604 or BGB-DXP593. The dose of study drug(s) will be based on the subject's actual body weight 1 day before the administration of study drug(s) (Day -1).

As a routine precaution, subjects must be monitored for ≥ 2 hours after the infusion of study drug(s) in an area with resuscitation equipment and emergency agents. The study drug(s) must not be administered concurrently with any other drug.

For safety reasons, the first 2 subjects randomized and dosed in each cohort will be monitored for ≥ 48 hours before the remaining subjects receive the same dose of study drug(s).

In this study, after the last subject in the current cohort has received the study drug and has been followed up for ≥ 5 days, the SMC will review the available safety and laboratory data. The next cohort will be initiated after the SMC review.

Accurate records of the study drug(s) received, dispensed, returned, and disposed of should be maintained in the site's Drug Inventory Log. Please refer to the Pharmacy Manual for details regarding study drug(s) management, drug preparation, storage, and administration.

5.3. Measures to Minimize Bias: Randomization and Blinding

Randomization

For each cohort, eligible subjects will be randomized at a 3:1 ratio (6 active: 2 control) to receive BGB-DXP604 with or without BGB-DXP593 or placebo. Sentinel dosing will be adopted for each cohort; the randomization ratios for sentinel dosing are provided in Section 3.1.

Site personnel will access the Interactive Response Technology (IRT) system to randomize the treatment assignment. All subjects will receive a unique study subject number. Up to 2 replacements will be allowed for each subject (eg, the original subject in one treatment arm is allowed to have a 2nd replacement when the 1st replacement is withdrawn). A subject for replacement will be assigned to the same treatment as the subject he/she replaces.

Blinding

The study is designed as double-blind for the subjects and the investigator (as well as the site personnel) in order to eliminate observational or performance bias. This is to avoid the systematic differences in assessments on the subject's treatment (ie, BGB-DXP604 with or without BGB-DXP593 or placebo).

The single dose of study drug(s) will be prepared by unblinded pharmacist(s) and administered by blinded study nurse(s). The intravenous infusion of BGB-DXP604, BGB-DXP593, and placebo will be colorless. All follow-up evaluations will be performed by blinded clinic staff.

At the study site, access to the treatment information for each subject is restricted to the unblinded pharmacist(s). Persons directly involved in the clinical conduct of the study will not have access to the treatment allocation before database lock.

Regarding the sponsor, the database of this study will be handled as open label, meaning that the study functions of the sponsor are unblinded (including the medical monitor and study team members from Pharmacovigilance/Drug Safety, Clinical Pharmacology, and Biostatistics with other members as appropriate). The objectives of the study are expected not to be affected.

Unblinding

1. Emergency unblinding

In case of an emergency, the investigator has the sole responsibility for determining if the unblinding of a subject's treatment assignment is warranted. Subject safety must always be the first consideration in making such a determination. Emergency unblinding for AEs may be performed through an IRT system.

If the investigator decides that unblinding is warranted, the investigator should make every effort to contact the medical monitor before unblinding a subject's treatment assignment unless this could delay emergency treatment of the subject. If a subject's treatment assignment is unblinded, the sponsor must be notified immediately.

2. Inadvertent unblinding

Every effort will be made to blind both the subject and the investigator to the identity of BGB-DXP604, BGB-DXP593, or placebo, but inadvertent unblinding of a subject may occur. If an investigator, site personnel performing assessments, or subject is unblinded, the unblinding will not be the sufficient cause for that subject to be discontinued from study or excluded from any analyses.

5.4. Incorrect Administration

Any incorrect administration of the study drug(s) should be noted in the subject's medical record and on the appropriate electronic case report form (eCRF).

AEs due to an incorrect administration of the study drug(s) will be recorded on the AE eCRF. Any SAEs associated with an incorrect administration must be reported within 24 hours of awareness via the SAE reporting process as described in Section 9.7.2. Supportive care should be administered as appropriate.

5.5. Dose Interruption or Modification

There will be no dose reduction of study drug(s).

A subject may temporarily interrupt their infusion of study drug(s) or discontinue their infusion of study drug(s) due to infusion-related reactions or other medical events.

The subject should resume the study treatment within 2 hours of the infusion interruption if the AE is resolved or recovered to Grade 1 (whichever is more severe). If the subject is unable to resume the study drug(s) within 2 hours of the infusion interruption, then the subject should be discontinued from the study treatment and the subject will be replaced. The treatment modification for infusion-related reactions is provided in Section 9.8.1.

6. PRIOR AND CONCOMITANT THERAPY

6.1. Prior Therapy

The exclusion criteria (Section 4.2) specify that:

- subjects must not have received any licensed or investigational biologic agent (such as monoclonal antibodies) within 3 months or 5 half-lives (whichever is longer) before randomization
- subjects must not have received any licensed or investigational nonbiologic agent (such as those derived from chemical synthesis) within 1 month or 5 half-lives (whichever is longer) before randomization
- subjects must not have received any over-the-counter or prescription medication, including herbal medications, within 28 days before randomization. Use of paracetamol, ibuprofen, and/or vitamins at the recommended dose will be allowed at the investigator's discretion within 28 days before randomization.

6.2. Concomitant Therapy

As healthy subjects are enrolled in the study, concomitant therapy is not allowed during the study. If medical events (such as infusion-related reactions or severe hypersensitivity) occur during the study period, the subjects may receive appropriate medical treatment. The management of infusion-related reactions and severe hypersensitivity is provided in Section 9.8.

All concomitant medications taken during the study will be recorded in the eCRF with indication and dates of administration.

6.3. Potential Interactions Between BGB-DXP604 or BGB-DXP593 and Concomitant Medications

The potential for drug-drug interaction between BGB-DXP604 or BGB-DXP593 and small-molecule drug products is very low, given that BGB-DXP604 and BGB-DXP593 are monoclonal antibodies. Because BGB-DXP604 and BGB-DXP593 are expected to degrade into amino acids and recycled into other proteins, they are unlikely to have an effect on drug metabolizing enzymes or transporters.

7. STUDY PERIODS, VISITS, OR PROCEDURES

Study periods, visits, and procedures are summarized in the following subsections. The timing of all study procedures is provided in the Schedule of Assessments ([Appendix 1](#)).

7.1. Screening Period

Screening evaluation will be performed within 28 days before administration of study drug(s). A subject who agrees to participate in this study will sign the informed consent form (ICF) before undergoing any study-specific procedures. Refer to Section [8.1](#) for instructions regarding screening assessments.

7.1.1. Informed Consent

Voluntary, written informed consent for participation in the study must be obtained before any study-specific procedures are performed. ICFs for enrolled subjects and for subjects who are screened but not enrolled will be maintained at the study site. Consent must be obtained using the most current version of the form approved by the IEC/IRB.

For subjects who provide informed consent and who subsequently do not meet eligibility criteria or who withdraw consent before administration of study drug(s), study site personnel should document this as a screen failure in the subject's source documents. The documentation should include demographics and medical history, the reason for screen failure, the eligibility criteria reviewed, procedures performed.

7.2. Enrollment

7.2.1. Confirmation of Eligibility

The investigator will assess and confirm the eligibility of each subject. All screening results and relevant medical history must be available before eligibility can be determined. All inclusion criteria must be met and none of the exclusion criteria may apply. No eligibility waivers will be granted.

7.2.2. Subject Numbering

After informed consent is obtained, a unique subject number will be assigned to a potential study participant.

7.3. Check-in (Day -1)

The enrolled subjects will be admitted ≥ 12 hours before the administration of study drug(s). On the day of admission, screening for alcohol/drugs, a review of the inclusion/exclusion criteria, laboratory assessments of hematology, clinical chemistry, coagulation, urinalysis, and safety assessments of vital signs and weight will be performed. Smoking will be not allowed during the inpatient stay.

7.4. Randomization

Site personnel will access the IRT system to randomize the treatment assignment. Randomization will occur after admission on Day -1 and before the administration of study drug(s) on Day 1.

7.5. Treatment (Day 1)

The enrolled subjects will be treated as described in Section 5.2. The study procedures on Day 1 are shown in Appendix 2. Refer to Section 7.7 for additional considerations regarding treatment withdrawal.

7.6. Follow-up Period

The follow-up period starts the next day after infusion of study drug(s) and continues until Day 113 of the study. All AEs, including SAEs, will be collected as described in Section 9.7.

7.6.1. Check-out (Day 3)

The subjects will be discharged 3 days after the administration of study drug(s). Before the discharge, the procedures and assessments specified in Appendix 1 should be completed.

7.6.2. End-of-Study Visit

Subjects who permanently discontinue from the study will be asked to return to the study center for the End-of-Study (EOS) Visit, which is required to be conducted ≤ 7 days after premature study discontinuation. The Day 113 Visit is the EOS Visit for subjects who complete all previously planned study visits.

If a subject refuses to return for the EOS Visit or is unable to do so, every effort should be made to contact the subject by telephone to determine their health status.

7.6.3. Safety Follow-up Visit for Premature Study Discontinuation

If a subject discontinues the study ≤ 30 days after the administration of study drug(s), a Safety Follow-up Visit will be conducted 30 days after study drug(s) administration. If premature discontinuation from study occurs ≤ 7 days before 30 days after the administration of study drug(s), the Safety Follow-up Visit may be combined with the EOS Visit if appropriate. A visit window of ± 3 days will be allowed for the Safety Follow-up Visit.

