2.2. Study Endpoints

2.2.1. Primary Endpoint

- Incidence and severity of treatment-emergent adverse events (TEAEs) and treatment-emergent serious adverse events (SAEs)

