9.7. Timing, Frequency, and Method of Capturing Adverse Events and Serious Adverse Events

9.7.1. Adverse Event Reporting Period

After informed consent has been signed but before administration of the study drug(s), only SAEs should be reported.

After initiation of the study drug(s), all AEs and SAEs, regardless of relationship to study drug(s), will be reported until 30 days after the administration of study drug(s) or the EOS Visit, whichever is later. After the period, the investigator should report any SAEs that are considered to be related to the study drug(s).

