10.3.2. Adverse Events

The AE verbatim descriptions (as recorded by the investigator on the eCRF) will be classified into standardized medical terminology using the Medical Dictionary for Regulatory Activities (MedDRA). AEs will be coded to MedDRA by the lowest level term, preferred term (PT), and primary system organ class (SOC).

A TEAE is defined as an AE that had an onset date or a worsening in severity from baseline on or after the administration of study drug(s) and ≤ 30 days after the administration of study drug(s). Only those AEs that were treatment emergent will be included in summary tables.

The incidence of TEAEs will be reported as the number (percentage) of subjects with TEAEs by SOC and PT. A subject will be counted only once by the highest severity grade according to NCI-CTCAE v5.0 within a SOC and PT, even if the subject experienced ≥ 1 TEAE within a specific SOC and PT. The number (percentage) of subjects with TEAEs will also be summarized by relationship to the study drug(s).

Treatment-related AEs include those events considered by the investigator to be related to study drug(s) or with missing assessment of the causal relationship. Treatment-emergent SAEs and treatment-related TEAEs will be summarized. All AEs, treatment-emergent or otherwise, will be presented in subject data listings.

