### 6.2. Data Analysis General Considerations

#### 6.2.1. Definitions and Computations

Study Day: study day will be calculated in reference to the date of the first dose of study drug. For assessments conducted on or after the date of the dose of study drug, study day will be calculated as (assessment date – the date of the dose of study drug + 1). For assessments conducted before the date of the dose of study drug, study day will be calculated as (assessment date – the date of the dose of study drug). There is no study day 0.

In the situation where the event date is partial or missing, the date will appear partial or missing in the listings. Study day and any corresponding durations will be presented based on the imputations specified in [Appendix A](#).

**Baseline:** baseline is defined as the last non-missing value collected before the first dose of study drug.

All subjects who received placebo from different cohorts will be pooled together into the placebo arm.

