### 6.5.2. Adverse Events

The AE verbatim descriptions (investigator terms from the eCRF) will be classified into standardized medical terminology using MedDRA. Adverse events will be coded to the MedDRA lowest level term closest to the verbatim term, along with the linked MedDRA PT and primary SOC.

A TEAE is defined as an AE that had an onset date or a worsening in severity from baseline on or after the administration of study drug and up to 30 days after the dose of study drug. Summary tables will generally focus on those AEs that were treatment-emergent. All AEs, treatment-emergent or otherwise, will be presented in subject data listings.

If any of the following TEAEs occurs, the administration of the study drug and the enrollment of new subjects will pause for the current cohort:

- One or more  $\geq$  Grade 4 TEAEs or treatment-emergent SAEs related to study drug(s) as assessed by the investigator in any subject or
- One or more Grade 3 TEAEs related to study drug(s) as assessed by the investigator in 2 or more subjects at the same cohort.

An AE overview table, including the number of subjects with TEAEs, TEAEs with grade 3, TEAEs with grade 4 or higher, treatment-emergent serious adverse events (SAEs), TEAEs that led to death, TEAEs that led to treatment discontinuation, TEAEs that led to treatment modification for study drug, and treatment-related TEAEs, will be provided by treatment group. Treatment-related AEs include those events considered by the investigator to be related to study drug or with a missing assessment of the causal relationship.

The incidence of TEAEs will be reported as the number (percentage) of subjects with TEAEs by SOC, PT and the worst grade. A subject will be counted only once by the highest severity grade according to [NCI-CTCAE version 5.0](#) within a SOC and PT, even if the subject experienced more than one TEAE within a specific SOC and PT. The number (percentage) of subjects with TEAEs will be summarized by SOC and PT.

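### For subjects who leave within 30 days of dosing, the last scheduled contact may fall 3 days before the 30-day TEAE window ends, so late events rely on spontaneous report (minor)

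*Protocol*

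**What the plan says.** The primary endpoint (Protocol Section 2.2.1) is the incidence and severity of TEAEs and treatment-emergent SAEs. SAP Section 6.5.2 counts an event as treatment-emergent if it starts or worsens "on or after the administration of study drug and up to 30 days after the dose of study drug"; Protocol Section 10.3.2 uses the same 30 days. Protocol Section 9.7.1 sets the collection period separately: all AEs and SAEs "will be reported until 30 days after the administration of study drug(s) or the EOS Visit, whichever is later".

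For subjects who discontinue the study at or before 30 days, Protocol Section 7.6.3 says that "a Safety Follow-up Visit will be conducted 30 days after study drug(s) administration". Two allowances follow:

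- When discontinuation falls in the 7 days before day 30, "the Safety Follow-up Visit may be combined with the EOS Visit if appropriate". Under Section 7.6.2 the EOS Visit is due within 7 days of discontinuation, with no minimum delay.
- "A visit window of ± 3 days will be allowed for the Safety Follow-up Visit".

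Appendix 1 footnote c repeats both allowances. Neither place requires the visit, separate or merged, to be held on or after day 30.

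**The concern.** For an early leaver, this visit is the only scheduled contact placed to cover the end of the TEAE window, yet it may be held before the window ends. The standard AE questions in Section 9.7.3 look back to the previous visit, so they cannot pick up an event that starts afterwards. A telephone call is specified only when the EOS Visit is not attended (Section 7.6.2).

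Subjects who stay in the study do not have this gap, because they are seen again at Day 43. Those who leave after day 30 have an EOS Visit after the window has closed.

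TEAEs are reported as the number and percentage of subjects. The SAP has no rule for a subject whose last contact precedes day 30, and SAP Section 6.2.3 imputes no missing data beyond partial dates. An event that is never reported therefore counts as no event, and the error can go only one way, towards fewer TEAEs.

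**Working it through.** The documents give no figure for this gap, so there is none to reproduce. Below, day n means n days after dosing. SAP Section 6.2.1 makes the dosing date Study Day 1 ("There is no study day 0"), so day 30 is Study Day 31.

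**1. Length of the gap** (30 minus the earliest permitted contact day)

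- Separate visit: 30 − 3 = day 27 (Study Day 28). Gap 30 − 27 = 3 days; 3/30 = 10.0% of the window.
- Merged visit, if ± 3 days does not apply to it: earliest qualifying discontinuation 30 − 7 = day 23, with the EOS Visit allowed the same day. Gap 30 − 23 = 7 days; 7/30 = 23.3%.
- Merged visit, if ± 3 days does apply: the gap is again at most 3 days.
- At the other end there is no gap: a separate visit can be as late as day 33, and a merged one as late as 30 + 7 = day 37 if only the EOS timing governs.

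**2. An ordinary route into the gap**

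Section 8.2.8 schedules a SARS-CoV-2 swab at Day 29, with a window of ± 1 day. That is 28 ± 1, or 27 to 29 days after dosing. A positive or suspected result means discontinuation from the study. If the result is known before day 30, the subject qualifies for a merged visit, which could be held 1 to 3 days before the window ends.

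**3. Chance that an affected subject's TEAE status is changed**

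Section 10.3.2 counts subjects, so overall TEAE incidence changes only if the subject's first TEAE falls in the gap. With 30-day risk p (assumed, since the documents give none), constant hazard and a gap of g days:

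P(first TEAE in gap) = (1 − p)^((30 − g)/30) − (1 − p)

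| Assumed p | g = 3 | g = 7 |
|---|---|---|
| 30% | 0.7^0.9 − 0.7 = 2.5% | 0.7^(23/30) − 0.7 = 6.1% |
| 50% | 0.5^0.9 − 0.5 = 3.6% | 0.5^(23/30) − 0.5 = 8.8% |
| 70% | 0.3^0.9 − 0.3 = 3.8% | 0.3^(23/30) − 0.3 = 9.7% |

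These are upper limits under the assumptions, because they suppose that nothing is reported spontaneously.

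**4. Size at study level**

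Planned enrolment is 3 × 8 = 24, giving 24 × 30 = 720 person-days. The number of early leavers is not given. If there were one, seen at the earliest day, 3/720 = 0.4% of person-days would lack a scheduled prompt, or 7/720 = 1.0% in the extreme case. With three, the figures are 9/720 = 1.3% and 21/720 = 2.9%.

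**The case against.** The strongest reply is that the protocol does not stop collecting events at the visit. Section 9.7.1, repeated in Appendix 1 footnote l, keeps the reporting duty open to day 30 whatever the visit date. Unscheduled visits are available for safety concerns (Section 8.5), and Section 9.8.2 tells subjects to report delayed reactions at once. This stands as far as it goes. A reader might infer that the last days go unobserved, or that the visit closes the TEAE window; the documents support neither. The window is fixed by date, and what is missing is a scheduled prompt. But an investigator can report only what is known, and after a compliant day-27 visit nothing requires anyone to ask.

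A reader might also take 7 days as the gap. That needs discontinuation and EOS Visit both on day 23, a decision that merging is suitable, and a reading in which ± 3 days does not govern the merged visit. In Section 7.6.3 the ± 3 sentence comes last and makes no exception, which suggests that it does govern. In footnote c the ± 3 days is attached to the separate visit, before merging is mentioned. Also, 23 + 7 = 30, so the merge rule picks out subjects whose EOS window can reach day 30, perhaps with a visit near that day in mind. The text does not settle the point, so 7 days is an extreme case only.

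A third tempting step is to take the chance of any event in the gap, 1 − 0.5^(3/30) = 6.7% or 1 − 0.5^(7/30) = 14.9%, and pair it with the shift from one missed subject among six active, 1/6 = 17 percentage points. The two do not belong together, because a subject already counted with a TEAE does not change overall incidence. The any-event figures could bear on a particular preferred term or a worst grade, but not on the overall count.

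Nor do the documents show that the loss falls on subjects who left for poor tolerability. Such a subject's AE is already recorded, and Section 9.4.4 requires it to be followed up. Finally, constant hazard may overstate late events after a single infusion, since infusion-related reactions come early.

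**Conclusion.** The point holds as a minor gap in ascertainment of the primary endpoint. For subjects who leave within 30 days, the protocol permits the last scheduled contact 3 days before the TEAE window and reporting period end. Seven days is possible only in the extreme case and on one reading of an unsettled rule.

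On an assumed 50% 30-day risk and constant hazard, the chance that an affected subject's first TEAE falls in the gap is about 3.6% (2.5% to 3.8% for risks of 30% to 70%), or 8.8% (6.1% to 9.7%) in the 7-day extreme. Any resulting error lowers TEAE incidence. It arises only for early leavers seen before day 30, and the analysis is descriptive with no hypothesis tested. It does not threaten the trial's conclusions. It is worth correcting because the documents give no reason for allowing the visit early and the correction is cheap.

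**What to change.** In Protocol Section 7.6.3, Appendix 1 footnote c and the Appendix 1 window row:

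- Change the Safety Follow-up Visit window from ± 3 days to 0/+3 days, that is, 30 to 33 days after dosing.
- State that a merged EOS/Safety Follow-up Visit counts as the Safety Follow-up Visit only if held on or after day 30. If the EOS Visit was earlier, ask about AEs by telephone on or after day 30.

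This reduces the interval without a scheduled prompt from 3 days (or 7 in the extreme case) to 0 for subjects who can still be contacted. It cannot help where a subject has withdrawn consent to contact or is lost to follow-up. The cost is a short text change, an occasional telephone call and slightly less scheduling flexibility for early leavers.
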